8.2 Secondary Endpoints

Secondary endpoints will be monitored and reported as in a full, randomized controlled trial. Endpoints will be defined in the following way.

8.2.1 Progressive or new VTE

All diagnoses of new or progressive VTE will require imaging confirmation, defined as intraluminal filling defect(s) on contrast-enhanced computed tomography (CT) or incompressible venous segment(s) on ultrasonography. In the absence of these studies, a new mismatched segmental defect or a greater perfusion defect compared with baseline on a ventilation/perfusion (V/Q) scan, will also be considered confirmatory. A diagnosis of progression will require unequivocal extension of thrombus on repeat imaging. Presence or absence of symptoms (including pain and swelling in the setting of VTE, pain, dyspnea, hypoxia, tachycardia or hypotension in the setting of PE) will be documented. Events will be independently adjudicated by physicians blinded to the predictor data.

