5.1.2 Disease may be measurable or non-measurable

5.1.3 Age \geq 18 years of age

5.1.4 Diagnosis of, symptomatic venous thromboembolism requiring therapeutic-dose anticoagulation (unfractionated or low-molecular weight heparin or oral anticoagulants) throughout the period of hematopoietic recovery.

5.1.5 Anticipated platelet count $\leq 50 \times 10^9/L$ for ≥ 5 days within 72 hours of enrollment

5.1.6 Ability to understand and the willingness to sign a written informed consent document

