7.2 Baseline/Pre-Treatment Assessment

The following procedures will be obtained at baseline before randomization to establish trial eligibility and allow patient characterization. Results of tests and/or procedures conducted as per standard of care will be used to determine study eligibility.

- Medical history including disease and treatment specifics of both the hematologic malignancy and the venous thrombosis, history of bleeding and anti-thrombotic therapy including anticoagulation and antiplatelet agents.
- Targeted physical exam for evidence of bleeding, thrombosis and volume status
- Most recent complete blood counts (assessed within 3 days of study day 0)
- Most recent coagulation assays, including PT, PTT (within one week of study day 0) and fibrinogen (if available).
- CT scan, V/Q scan, Doppler ultrasound or other appropriate diagnostic modality to document VTE diagnosis.

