8.2.2 Progressive or new ATE

Diagnoses of new ATE will require either (1) documented acute electrocardiographic (EKG) changes compatible with myocardial injury and/or serum biochemical changes diagnostic of myocardial infarction (2) documented imaging (CT or magnetic resonance imaging (MRI)) changes compatible with infarct due to embolism in the presence of a new neurological deficit (3) imaging demonstrated intraluminal filling defects in an arterial distribution accompanied by symptoms of acute ischemia (acute onset pain, pallor, loss of pulses or other end-organ damage).

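### The VTE outcome accepts fewer imaging modalities than entry does, so progression seen only on an unlisted modality is excluded or ambiguous and a PE shown only at autopsy cannot count

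*Combined protocol and SAP*

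**What the plan says.** **Entry.** Section 5.1.4 requires "symptomatic venous thromboembolism requiring therapeutic-dose anticoagulation" and limits neither the site of the clot nor the test that shows it. Section 7.2 lists the documentation as "CT scan, V/Q scan, Doppler ultrasound or other appropriate diagnostic modality to document VTE diagnosis". That list is open.

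**Outcome.** Section 8.2.1 begins "All diagnoses of new or progressive VTE will require imaging confirmation", and the confirmation is "defined as intraluminal filling defect(s) on contrast-enhanced computed tomography (CT) or incompressible venous segment(s) on ultrasonography". V/Q is a fallback: "In the absence of these studies, a new mismatched segmental defect or a greater perfusion defect compared with baseline". For progression there is a further condition: "A diagnosis of progression will require unequivocal extension of thrombus on repeat imaging". That sentence names no modality. The section closes with "Events will be independently adjudicated by physicians blinded to the predictor data". It has no route for another modality or for autopsy.

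**Use.** New or progressive VTE is a secondary endpoint and part of the composite with ATE and bleeding (3.1.2, 3.3.2). Section 8.2 says the secondary endpoints are handled as they would be in a full randomised trial. Section 13.2 on endpoints and analytical methods restricts their analysis to descriptive statistics.

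**The concern.** A patient can enter with a clot documented by a test that the outcome definition does not name. If that clot grows and the growth is seen only on the same test, the adjudicators have two sentences that point different ways. The opening of 8.2.1 restricts the modality for every diagnosis, while the progression sentence asks only for repeat imaging. Two adjudicators could reasonably classify the same event differently.

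Autopsy is clearer. A pulmonary embolism found only at autopsy has no imaging, so it fails the opening requirement. Appendix 3 counts fatal bleeding from any source as grade 4, so one component of the composite captures its fatal events and the other can miss them. Death is not among the listed secondary endpoints and appears only as a serious adverse event outcome (10.2.3).

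At stake is the completeness of the VTE and composite counts. Because the pilot reports outcomes as a definitive study would, the definition may also be carried into the later trial.

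**Working it through.** The plan states no figure on this point, so the check is mainly a comparison of text.

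**1. Entry and outcome side by side**

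| How the thrombosis is shown | Index VTE (7.2) | New or progressive VTE (8.2.1) |
|---|---|---|
| CT | accepted | accepted (filling defect, contrast CT) |
| Ultrasound | accepted | accepted (incompressible segment) |
| V/Q | accepted | accepted if CT and ultrasound are absent |
| Any other suitable modality | accepted | not listed; for progression, the repeat-imaging sentence is silent |
| Autopsy only | not applicable | no route |

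**2. Which patients lose an event**

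- Entered on an unlisted modality, restudied by CT or ultrasound (or V/Q as fallback), new thrombosis found: counts. Section 8.2.1 does not require the modality used at entry.
- Same patient, with unequivocal extension of the old clot on a listed modality: can count, although comparison across modalities may make unequivocal extension harder to show.
- Same patient, extension seen only on the unlisted modality: excluded or ambiguous.
- PE found only at autopsy: does not count.

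Only the last two cases are lost or unclear.

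**3. Size**

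The documents give neither the share of index clots shown by another modality nor a rate of progression or recurrence. The following ranges are assumptions for scale:

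- a = share of patients entering on an unlisted modality: 5% to 15%.
- b = share of patients with progression or recurrence: 5% to 10%.
- Events at risk of being missed = N × a × b.

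Pilot, N = 12 (synopsis):

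- low: 12 × 0.05 × 0.05 = 0.03
- high: 12 × 0.15 × 0.10 = 0.18

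Later trial, N = 2 × 125 = 250 (section 13.2, sample size):

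- low: 250 × 0.05 × 0.05 = 0.6 (of 250 × 0.05 = 12.5 events)
- high: 250 × 0.15 × 0.10 = 3.8 (of 250 × 0.10 = 25 events)

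Under these ranges the results are upper bounds for the modality gap, because the formula treats every event in such patients as lost and step 2 shows that many would still count. PE shown only at autopsy is not in these figures, and the documents give no rate for it.

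**4. Does it reach a powered comparison?**

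The sample size section powers the later trial on WHO grade 2 or higher bleeding, with 40% or 60% bleeding and a relative risk of 1.4. No VTE rate enters that calculation, so a change to 8.2.1 changes none of its figures.

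**The case against.** The strongest reply is that the two sections do different jobs. Section 7.2 uses standard-of-care results to establish eligibility and describe patients, while 8.2.1 sets an objective outcome for blinded adjudication in an unblinded trial. An outcome that is stricter than entry documentation is a legitimate choice. This stands as a reason not to copy the open entry list into 8.2.1. It does not settle the unclear progression sentence or the missing autopsy route.

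A second reply is that the information is collected anyway. Chart review includes vascular imaging data without limit of modality (8.1.3), and thrombosis history is taken at follow-up (Appendix 2). Thrombosis that requires a change in antithrombotic management is a documented reason for ending active treatment (9.1.7). This also stands: in 12 patients such an event would probably be noticed. It could still be missing from the endpoint count, so a patient could leave active treatment for progressive VTE and have no VTE event under 8.2.1.

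Three stronger readings are tempting, and the documents do not support them:

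- *That no event can be counted in patients who entered on another modality.* Restudy by CT, ultrasound or V/Q counts, so sensitivity is reduced, not absent.
- *That undercounting pulls a non-inferiority comparison toward no difference.* The only non-inferiority comparison described is for bleeding. VTE is descriptive here. Equal under-detection in both arms, without false positives, would also leave a relative risk unchanged in expectation and shrink only the absolute difference.
- *That the ATE definition is inconsistent with the VTE definition because it accepts MRI.* Section 8.2.2 reads "documented imaging (CT or magnetic resonance imaging (MRI)) changes compatible with infarct", which concerns infarct with a new neurological deficit. That is a different diagnosis needing different tests.

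**Conclusion.** The point holds in a limited form. The outcome list in 8.2.1 is narrower than the entry list in 7.2. Progression seen only on an unlisted modality is excluded or ambiguous, and a PE shown only at autopsy cannot count toward the VTE endpoint or the composite, although fatal bleeding counts.

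The number affected is not given. In this pilot it is probably well under one event. The figure of 0.03 to 0.18 for the modality gap rests on assumed rates, and the autopsy part rests on judgement because no rate is available. The feasibility endpoints and the bleeding power figures are untouched. This is a cheap improvement, worth making mainly because the definition may be reused.

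**What to change.** Add to 8.2.1:

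- progression may be confirmed by unequivocal extension on the same modality that documented the index VTE;
- autopsy-proven PE counts as a VTE event, and so enters the composite;
- both remain subject to the existing independent, blinded adjudication.

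If other modalities are to be accepted for new VTE, name them as a closed list. Do not refer back to the open wording of 7.2, which would loosen the outcome in an unblinded trial.

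The cost is a sentence or two of text and no added imaging. The downside is a slightly broader definition that leans a little more on the adjudicators.

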8.2.2 Progressive or new ATE

Diagnoses of new ATE will require either (1) documented acute electrocardiographic (EKG) changes compatible with myocardial injury and/or serum biochemical changes diagnostic of myocardial infarction (2) documented imaging (CT or magnetic resonance imaging (MRI)) changes compatible with infarct due to embolism in the presence of a new neurological deficit (3) imaging demonstrated intraluminal filling defects in an arterial distribution accompanied by symptoms of acute ischemia (acute onset pain, pallor, loss of pulses or other end-organ damage).

8.2.3 Hemorrhagic events (WHO grade 2, 3 or 4)

Hemorrhagic events will be defined according to the WHO bleeding criteria (Appendix 3). Grade 3 events will be defined as events requiring packed red cell transfusions over and above the subject's routine transfusion needs. This will be determined based on the clinical judgment of an investigator.

8.2.4 Number of platelet transfusions

Only transfusions administered during the study period will be included. Transfusions administered 'off protocol' or inappropriately while 'on protocol' will also be counted. Type (apheresis unit or pooled packs) and volume of transfusion will also be noted.

8.2.5 Platelet transfusion related complications

Platelet transfusion reactions will be defined as any of the following (1) new onset fever, chills, hypoxia, urticarial rash or hemodynamic instability during or within 1-2 hours of administration of a transfusion with or without hemolysis (2) transfusion related lung injury (TRALI) defined as new onset dyspnea/tachypnea and hypoxia within 6 hours of transfusion, accompanied by bilateral pulmonary edema on imaging, with or without fever and hypotension.

Volume overload will be defined as evidence of edema (pulmonary, extremity or other dependent area) on exam and/or imaging, requiring treatment with diuretics and/or dialysis. Contribution of platelet transfusions to volume overload will be determined based on the clinical judgment of an investigator.

Alloimmunization will be defined as a combination of platelet refractoriness (as defined in section 7.6) accompanied by a panel reactive antibody result of >25%.

8.2.6 Percent of days on which subjects are transfused (or transfusions are not given) in compliance with the threshold to which they were randomized

Study staff will determine the appropriateness of transfusion management (in accordance with the protocol) each on-protocol day of the study period. The frequency with which transfusions are given despite a platelet count above the determined threshold (not including 72 hour temporary increases or procedures as outlined in section 7.6) will be documented, as will the frequency with which transfusions are not administered within 24 hours after a platelet count below the determined threshold.

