2.2 Clinical Data to Date

A recent survey of malignant/nonmalignant hematologists and transfusion medicine experts about this topic found a marked degree of variation in proposed transfusion thresholds (ranging from 25 to $50 \times 10^9/\text{L}$).⁵ A recent retrospective study of eighty-two SCCA patients with VTE during a period of treatment-related thrombocytopenia demonstrated that most providers here manage VTE with therapeutic anticoagulation, adjusting the platelet transfusion goal to $50 \times 10^9/\text{L}$, often resulting in two or more weeks of frequent platelet transfusions, potentially repeated in future treatment cycles. Bleeding rates (WHO grade 2 or above) were noted to be somewhat higher than those previously reported in the literature (37% at 30 days), but comparable to or less than rates expected in patients with severe treatment related thrombocytopenia (transfusion threshold $10 \times 10^9/\text{L}$), which is as high as 70% over a period of 30 days or less.⁶ While retrospective assessments of bleeding, particularly grade 2 bleeds, are limited and some bleeds are likely missed by this method, we expect this rate of bleeding is more representative of actual outcomes than those previously reported in the literature.

Our retrospective review demonstrated that the vast majority of patients at our institution in this situation are transfused to maintain a platelet count $\geq 50 \times 10^9/\text{L}$, with the above noted bleeding rate. The majority of bleeds occurred during a time when the platelet count was at or above this goal (mean $52 \times 10^9/\text{L}$) although the retrospective nature made it impossible to define or compare 'at risk' times. We did, however, note a number of transfusion related complications with this strategy including transfusion reactions in 13% of patients and volume overload requiring diuretic therapy or dialysis in 37% of patients.

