8.1.3 On-Study Visit Procedures

The following tests and procedures are completed, although not all tests may be done at each visit.

- Targeted history for symptoms of bleeding or thrombosis
- Targeted physical exam for symptoms of bleeding or thrombosis, volume overload
- Most recent complete blood counts (assessed within one day)

- FACT-Th18 Questionnaire (Appendix 5) will be completed weekly
- Bleeding diary (Appendix 4) will be reviewed at each visit and collected weekly
- Additional chart review including but not limited to documentation of suspected hemorrhage, thrombosis and/or transfusion reaction, transfusion administration, vascular imaging data, administration of anticoagulants, antiplatelet agents, antifibrinolytic or other pro-coagulant therapies and/or diuretics, dialysis for volume overload.

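### Section 8.2.5 defines platelet transfusion reactions by sign and timing alone, and its lung-injury branch does not exclude volume overload, so coincidental signs and acute overload can be reported as reactions

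*Combined protocol and SAP*

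**What the plan says.** Section 8.2.5 gives two alternative routes to a platelet transfusion reaction.

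- **Branch 1:** "new onset fever, chills, hypoxia, urticarial rash or hemodynamic instability during or within 1-2 hours of administration of a transfusion". Hemolysis is not required.
- **Branch 2:** "transfusion related lung injury (TRALI) defined as new onset dyspnea/tachypnea and hypoxia within 6 hours of transfusion, accompanied by bilateral pulmonary edema on imaging". Neither a raised temperature nor low blood pressure is required.

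Neither branch asks whether the transfusion caused the sign or whether another cause is more likely.

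The next paragraph treats volume overload differently. Its definition reads: "Volume overload will be defined as evidence of edema (pulmonary, extremity or other dependent area) on exam and/or imaging". The edema counts only if diuretics or dialysis are needed. A causal step then applies: "Contribution of platelet transfusions to volume overload will be determined based on the clinical judgment of an investigator".

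Section 3.3.2 lists reactions (7a) and volume overload (7c) as separate sub-items. Section 13.2 (Primary/Secondary Endpoints) limits all secondary endpoints to descriptive statistics. Sections 3.1.2 and 8.2 say they are to be reported as they would be in a full trial. For background, section 2.2 reports "transfusion reactions in 13% of patients and volume overload requiring diuretic therapy or dialysis in 37% of patients" in the institution's retrospective series and a median of 6 transfusions over 30 days.

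**The concern.** Patients on leukemia chemotherapy or after allogeneic transplant have many reasons for new fever, hypoxia or hypotension. Under branch 1, an infectious fever that starts an hour after a platelet unit is a transfusion reaction. The same fever on a day without a transfusion is not. The randomized threshold is meant to change how many transfusions are given, so it also changes how many windows exist in which a coincidental sign can be counted. The resulting error has a direction: it adds more false reactions to the arm with more transfusions. Section 2.3 hypothesizes fewer transfusion-related complications at the lower threshold, and the error leans the same way.

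The second problem is classification. Overload that shows itself as dyspnea, hypoxia and bilateral pulmonary edema within 6 hours, and is treated with diuretics, satisfies branch 2 and the overload definition together. It would then be reported once as lung injury and once as overload.

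At stake is the meaning of a descriptive secondary endpoint, and of a definition that may carry over to the larger trial. The pilot's primary result is not at stake.

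**Working it through.** The documents give no figure for this endpoint that can be reproduced, so the check is a comparison of the text followed by an illustration.

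**1. The definitions side by side**

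| | Time limit | Relatedness step | Excludes the other category |
|---|---|---|---|
| Reaction, branch 1 | 1-2 hours | none | no |
| Reaction, branch 2 (TRALI) | 6 hours | none | no |
| Volume overload | none | investigator judgment | no |

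Pulmonary edema with hypoxia within 6 hours, treated with diuretics, fits rows 2 and 3. New hypoxia from overload inside the 1-2 hour window fits row 1 as well. Extremity edema alone fits only row 3.

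**2. Coincidental signs**

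From section 2.2: n = 6 transfusions per patient. Assumed, because the documents do not give them: a window of 3 hours per transfusion (1 hour of infusion plus 2 hours), a background onset of any listed sign of 0.05 to 0.2 per patient-day, and n = 3 at the lower threshold.

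P(at least one coincidental reaction) = 1 - exp(-rate x n x 3/24)

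| Rate per day | n = 3 | n = 6 | Ratio | Gap in patients, arms of 6 |
|---|---|---|---|---|
| 0.05 | 1.9% | 3.7% | 1.98 | 0.11 |
| 0.1 | 3.7% | 7.2% | 1.96 | 0.21 |
| 0.2 | 7.2% | 13.9% | 1.93 | 0.40 |

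For example, at 0.1 per day and n = 6: 1 - exp(-0.1 x 6 x 0.125) = 1 - exp(-0.075) = 7.2%. The gap is 6 x (7.2% - 3.7%) = 0.21. Doubling the transfusions nearly doubles the coincidental share.

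**3. The unfixed window**

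Reading the limit as 1 hour instead of 2 makes the at-risk time 2 hours instead of 3. At 0.1 per day and n = 6 this gives 1 - exp(-0.1 x 6 x 2/24) = 1 - exp(-0.05) = 4.9%, against 7.2%.

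**4. Per transfusion**

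The expected number of coincidental onsets per transfusion at 0.1 per day is 0.1 x 3/24 = 0.0125, or 1.25 per 100, whatever n is. A per-transfusion rate is therefore not tilted by the number of transfusions.

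**5. Overlap**

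If 10-30% (assumed) of the historical 37% with overload met branch 2, then 0.37 x 0.10 = 3.7 and 0.37 x 0.30 = 11.1 percentage points of patients would also be listed as TRALI.

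**The case against.** The strongest reply is that little turns on this. Reactions are one sub-item of a secondary endpoint, described without any test, in about six patients per arm. Enrollment and compliance decide feasibility, and the full trial's primary outcome would be bleeding. That stands, and it sets the severity.

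The inputs can also be challenged. The onset rate, window, halving of transfusions and overlap fraction are all assumptions. The top value of 13.9% from coincidence alone exceeds the 13% historical reaction rate, so the upper end is doubtful unless the retrospective series defined reactions more narrowly, which the documents do not say. True reactions also rise with transfusions, so only the coincidental share is error. This stands too.

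There are partial safeguards. The sign must be new, section 5.2.9 excludes active infection at entry, and chart review in section 8.1.3 looks for "documentation of suspected hemorrhage, thrombosis and/or transfusion reaction", so capture may run through clinician suspicion. But suspicion is a data source there and not a condition of the endpoint, and the entry criterion does not prevent fever on study. Blinded review, "Events will be independently adjudicated by physicians blinded to the predictor data", is written only under VTE in section 8.2.1.

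A reader might infer three stronger points that the text does not support:

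- **Red-cell reactions are counted.** Branch 1 says only a transfusion, but the section heading and the opening of the sentence both specify platelets. This is loose wording at most.
- **Overload inflates a total by being scored twice.** No summed complication endpoint exists. The only composite in section 3.3.2 covers VTE, ATE and hemorrhage.
- **The rule manufactures the trial's main hypothesized benefit.** Sections 2.3 and 2.4 list complications beside patient burden, cost and resource use without ranking them, and no comparison is tested.

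**Conclusion.** The point holds as a minor one. As written, section 8.2.5 reports a coincidental sign in the window as a reaction, and allows an acute overload episode to be reported as lung injury under 7a and again under 7c. The coincidental share rises almost in step with the number of transfusions and so tends to favor the 30 arm, provided that arm does receive fewer transfusions.

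The size is unknown. Under the assumed rates it is about 2-14% of patients, with a gap between arms of less than half a patient in this pilot. The overlap is 3.7-11.1 percentage points if 10-30% of historical overload would meet branch 2. The feasibility conclusion and the stated sample size do not change. The reason to act is that these outcomes are meant to be reported as in a definitive trial.

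**What to change.** In section 8.2.5:

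1. Add to the TRALI branch that the episode is not explained by volume overload, and assign each episode to one category. The one-category rule is needed because hypoxia from overload can also enter through branch 1.
2. State one time window in place of 1-2 hours, and specify a platelet transfusion in both branches.
3. Report reactions per platelet transfusion as well as per patient. The per-patient figure keeps any real benefit of fewer transfusions visible. The per-transfusion figure shows whether the difference is more than exposure.
4. If a relatedness step is added, have it judged from records with the arm masked where possible, and also report the count under the sign-and-time rule. The trial is open label, so an unmasked judgment would exchange one bias for another. Masking means leaving the pre-transfusion platelet count out of the extract, because a transfusion at a count between 30 and 50 points to the 50 arm.

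The cost is a few lines of wording and slightly more review work. Section 8.2.4 already counts every platelet transfusion in the study period, and the chart review in section 8.1.3 already covers transfusion administration and suspected reactions. The reported reaction count would probably be somewhat lower.

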3.3.2 Secondary Endpoints

1. Progressive or new VTE
2. Progressive or new ATE
3. Hemorrhagic events (WHO grade 2 or greater)
4. A composite of a, b and c.
5. Major bleeds (WHO grade 3 or 4)
6. Number of platelet transfusions per patient during the study period
7. Platelet transfusion related complications
 - a. transfusion reactions
 - b. alloimmunization
 - c. volume overload
8. Percent of days on which subjects are transfused (or transfusions are not given) in compliance with the threshold to which they were randomized

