7.7 Duration of Therapy

Patients will remain on protocol until (1) the platelet count spontaneously recovers to $>50 \times 10^9$ for three consecutive days, in the absence of transfusions or (2) for a maximum of 30 days after the date of randomization, whichever is shorter. The study period is defined as the period between the first on-study day (post-randomization) with platelet count $<50 \times 10^9$ and either of these endpoints regardless of whether the patient receives transfusions according to protocol or not. Following conclusion of the study period, transfusion thresholds will be determined by each subject's primary provider.

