7.7.1 Breaking Randomization

Randomization may be broken and the patient taken off protocol for any of the following reasons. In all cases the new threshold will be noted and the patient will be observed for primary and secondary outcomes until the completion of the study period.

Randomization will be immediately broken and transfusions managed according to the subject's managing provider(s) for any grade 3 or 4 bleeding event. The new threshold will be noted and the patient will be followed for outcomes until the end of the study period. If a grade 3 event completely resolves in <72 hours, is non-life-threatening, does not require permanent discontinuation of anticoagulation and is not reasonably expected to recur (eg vaginal bleeding resolved with hormonal therapy, bleeding from a wound which has been closed), the patient and primary provider may elect to continue with the randomized threshold.

For subjects in whom discontinuation of anticoagulation is deemed necessary by managing providers, randomization will be broken, and a new transfusion threshold will be determined at the discretion of the managing team.

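### Section 8.2.6 scores day-level threshold compliance only on on-protocol days, so the percentage does not register patients who leave their randomized threshold

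*Combined protocol and SAP*

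**What the plan says.** - **Endpoint as listed (3.3.2, item 8).** "Percent of days on which subjects are transfused (or transfusions are not given) in compliance with the threshold to which they were randomized". Nothing here limits which days count.
- **Endpoint as defined (8.2.6).** "Study staff will determine the appropriateness of transfusion management (in accordance with the protocol) each on-protocol day of the study period". Two kinds of deviation are then recorded: transfusions given above the threshold, and transfusions not given within 24 hours of a count below it. The first excuses some cases: "not including 72 hour temporary increases or procedures as outlined in section 7.6".
- **Study period (7.7).** It runs from the first post-randomization day with a count below 50 to count recovery or 30 days from randomization. It ends at "either of these endpoints regardless of whether the patient receives transfusions according to protocol or not".
- **Leaving the arm (7.7.1).** "Randomization may be broken and the patient taken off protocol for any of the following reasons". Afterwards, "In all cases the new threshold will be noted", and the patient is observed for primary and secondary outcomes to the end of the study period. Section 9.2 says the same, except after withdrawal of consent.
- **Primary compliance measure.** Section 3.3.1 counts patients being transfused on protocol at the end of the study period. Section 8.1 (Primary Endpoint) calls that proportion a second key measure of feasibility, and 13.2 (Analytical Methods) refers to 3.3.1 for compliance. The synopsis sets the bar at 70% or more without saying whether the unit is patients or days.

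**The concern.** A day can belong to the study period without being an on-protocol day: every day between a formal break of randomization and the end of the study period is of this kind. Under 8.2.6 those days are not scored. Being counted therefore depends on still being managed under the assigned arm, and a patient who leaves on day 5 contributes only the days before leaving.

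At stake is what the pilot can say about separation, meaning for how much of the thrombocytopenic period the two groups were really managed at 30 and at 50. The endpoint's title promises that, but the definition delivers adherence among patients who have not yet left. A reader who takes the title at its word will think the arms were further apart than they were.

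**Working it through.** **1. The plan's own figures.** The plan derives no compliance figure, and the 70% bar is set without calculation. The one derived figure nearby is the power of the future trial (13.2, Sample Size and Power): 125 per arm, 40% bleeding in both arms, margin 0.16, one-sided 0.05.

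SE = √(2 × 0.4 × 0.6 / 125) = 0.0620. Power = Φ(0.16/0.0620 − 1.645) = Φ(0.94) = 82.6%. Exact enumeration gives 83.4%, against about 84% stated, so it reproduces. It contains no compliance term.

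**2. Which days count where.**

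| Day | 8.2.6 | Title in 3.3.2 | Primary (3.3.1) |
|---|---|---|---|
| On protocol, managed as assigned | scored, compliant | compliant | not day-based |
| On protocol, unexcused deviation | scored, non-compliant | non-compliant | not day-based |
| After a formal break | not scored | scored against randomized threshold | patient fails if off protocol at the end |

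Only the third row differs between the definition and the title.

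**3. Size.** From the documents: 12 patients and a study period of at most 30 days. Assumed: all study periods have the same length L; 95% of on-protocol days are compliant, for leavers as for others; k patients leave after day d; a fraction c of later days still agrees with the randomized threshold.

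- 8.2.6 figure = 95% for every k and d.
- On-protocol days = (12 − k)L + kd. Later days = k(L − d).
- All-days figure = [0.95 × on-protocol days + c × later days] / 12L.
- Patient-level figure = (12 − k)/12.

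| L | k | d | On-protocol / later days | 8.2.6 | All days, c = 0 | All days, c = 0.5 | Patients on protocol at end |
|---|---|---|---|---|---|---|---|
| 30 | 3 | 5 | 285 / 75 | 95% | 75.2% | 85.6% | 75.0% |
| 30 | 4 | 5 | 260 / 100 | 95% | 68.6% | 82.5% | 66.7% |
| 30 | 6 | 5 | 210 / 150 | 95% | 55.4% | 76.3% | 50.0% |
| 30 | 6 | 15 | 270 / 90 | 95% | 71.3% | 83.8% | 50.0% |
| 30 | 8 | 5 | 160 / 200 | 95% | 42.2% | 70.0% | 33.3% |
| 14 | 6 | 5 | 114 / 54 | 95% | 64.5% | 80.5% | 50.0% |

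Worked line (k = 6, d = 5, L = 30): 0.95 × 210 / 360 = 55.4%; adding 0.5 × 150 / 360 = 20.8 points gives 76.3%.

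The value c = 0 is an extreme. On a day with a count below 30 or above 50, both thresholds call for the same action, so some later days will agree by chance. The all-days figure is lower than the 8.2.6 figure whenever c is below 95%.

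**4. What the patient count adds and does not add.** Read as a proportion of 12 patients, 70% needs 9 (75.0%), since 8/12 = 66.7% falls short. Four patients off protocol at the end therefore fail it. But six leavers give 50.0% whether they go at day 5 or day 15, while the all-days figure (c = 0) moves from 55.4% to 71.3%. The patient count records that patients left, not how long they were managed as assigned.

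**The case against.** The best defence is that the plan describes two things separately and coherently: retention, through the patient-level primary measure, and fidelity while assigned, through 8.2.6. After a break the threshold is at the provider's discretion under the protocol, so scoring those days as failures would blur a permitted exit with a lapse. All secondary endpoints are descriptive. Much of this stands, and it rules out several stronger readings that a reader might infer:

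- *The pilot as a whole could report high compliance while many patients are off their arm.* Not supported. The primary measure counts those patients and misses 70% at four of 12. The synopsis leaves the unit of the 70% open, but 13.2 points to the patient-level definition.
- *Every day away from the assigned threshold disappears.* Not so. Deviations while on protocol are scored, apart from the excused temporary increases and procedures. Only days after a formal break are lost.
- *Section 8.2.6 contradicts 7.7 and 8.2.4.* It does not. Section 7.7 defines the period and 8.2.6 takes a subset of it. Section 8.2.4 measures transfusion burden, a different endpoint, so its rule "Transfusions administered 'off protocol' or inappropriately while 'on protocol' will also be counted" does not bind 8.2.6. The real tension is with the unrestricted title in 3.3.2 and with 7.7.1, which follows secondary outcomes to the end of the study period.
- *The full trial would be mis-sized.* The table in 8.1 uses eligible patients and consent rate, and the power calculation has no compliance input. Compliance appears in 13.2 only as a general factor in judging feasibility.
- *The overstatement differs by arm.* This is plausible, since reasons for exit may differ, but the documents give no rates from which to show it.

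What the defence does not answer is the title. The endpoint is presented as compliance with the randomized threshold by day, and neither measure in the plan reports that over the whole study period.

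**Conclusion.** The point holds for the secondary day-level endpoint only. As defined, it does not respond to exits, however many or however early. In the cases above it reads 95% where compliance with the randomized threshold over all study-period days is between 42.2% and 85.6%. Those figures rest on assumed exit numbers, exit times, period lengths, later agreement and on-protocol compliance. They show how far the two denominators can part, not what this pilot will observe. The patient-level primary measure limits the damage to the feasibility conclusion but cannot supply the missing information on duration. For a descriptive secondary endpoint in a 12-patient pilot, severity is minor to moderate.

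**What to change.** In 8.2.6, define the main figure as compliance with the randomized threshold over every study-period day as set out in 7.7, whether or not randomization has been broken, excluding days after withdrawal of consent. Report it by arm. Calculate each patient's percentage first and then summarize across patients, so that one 30-day patient does not outweigh several short ones. Beside it, show the on-protocol-days figure and the number and timing of breaks, so that permitted exits and lapses remain distinguishable.

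The cost is a sentence or two in 8.2.6 and slightly more analysis. The new threshold is already noted after a break (7.7.1), off-protocol transfusions are already counted (8.2.4), and Appendix 2 lists daily platelet count and threshold. Appendix 2 places these under active management, so it should say that their collection continues after a break. The downside is a lower reported compliance figure. Patient care does not change.

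While editing, it would help to state in the synopsis that the 70% criterion is a proportion of randomized patients, in line with 3.3.1 and 13.2.
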